Study Title:

**Efficacy of Tranexamic Acid in reducing requirement of blood transfusion
in Lower Limb Trauma Surgery: A prospective randomized controlled study**

Date: 05th July, 2021

Study Protocol

This study was a single-centre, randomized controlled parallel group study with 1:1 allocation. After obtaining ethical approval from IEC (**Ref No. PHMA/GSMCH-17/IEC-29A**), 116 patients of lower limb trauma presenting to Emergency Department of Civil Hospital, Rajpura between April 2017 to August 2018 were taken up for the study. Written informed consent was obtained from all the participating patients.

Patient selection

The patients, aged 18-60 years, suffering from lower limb trauma were taken up for the purpose of the study. The presence of old implant or infection at the fracture site, or any blood coagulation disorder were the exclusion criteria for the study. The patients undergoing percutaneous wire placement procedures for fracture fixation were also excluded from the study. The other exclusion criteria were polytrauma, non-consenting patients, psychiatric patient. 16 patients were excluded due to old fracture, percutaneous wire fixation or non-consenting patient. A total of 100 patients met the inclusion criteria and were enrolled.

Pre-operative evaluation

The enrolled patients were assessed preoperatively and all relevant investigations done. The patients were taken up for surgery after stabilization of the general condition. Pre-operative blood transfusion was done as required to have Hb level of at least 9.5mg/dl.

Surgical intervention

The patients were administered spinal anaesthesia or general anaesthesia, depending on the anaesthetist's discretion. The patients were treated by internal fixation of fracture by means of plates or interlocking nails. They were given antibiotic prophylaxis at the beginning of surgery. Intra-operatively, all the patients were given Ringer Lactate and intravenous colloid solution (Haemaccel) for volume replacement.

The patients enrolled were randomly divided into 2 groups. The random allocation of the patients to either group was done by one of the authors using a random number table. Group Tranexamic Acid (Group A) had 50 patients who were given 1 gram of TXA intravenously pre-operatively. IV TXA was administered, at the time of start of surgical incision, by mixing 1 g of TXA in 100 ml of normal saline. Control group (Group B) had 50 patients which were kept as a control group and were not given TXA.

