Post-operative evaluation

The requirement of number of units of blood transfusion post-operatively was recorded as a primary outcome measure. The post-operative blood transfusion was done if the patients' Hb level fell below 9.5 mg/dl. The secondary outcome measures included change in Haemoglobin level, total length of hospital stay and the evidence of deep vein thrombosis by Wells score. Patients of both groups were monitored by checking Haemoglobin (Hb) level as required. The Hb readings were expressed as mean \pm Standard Deviation and range.

Other complications were monitored daily by looking for leg swelling for DVT, breathlessness and fall in saturation for pulmonary embolism, or a cardiac event

like angina or myocardial infarction, deterioration of mental status for stroke event. In case the patient would have any of these complaints, a medical opinion was sought and managed accordingly.

The probability of venous thromboembolism was suspected by use of Wells et al Clinical model to assess pre-test probability of DVT. Patients with a high probability were to be administered D-Dimer test and other relevant tests as needed to confirm thromboembolism.

No prophylactic treatment for DVT was planned. All the patients were monitored for development of DVT and treatment to be given for symptomatic cases only.

Renal function tests (RFTs) were done post surgery and at discharge. If the level of serum creatinine was elevated to above 1.4 mg/dl or the level of Blood Urea Nitrogen was higher than 25 mg/dl, then elevated RFT level was diagnosed and medical consultation was ordered.

Sample size calculation

Sample size was calculated based on a clinically significant effect with atleast 25% reduction in need of blood transfusion in the post-operative period. Assuming requirement of blood transfusion in control and intervention group to be 15% and 40% respectively, with a two-sided significance of 0.05 and a power of 80%, a total of 49 patients in each group would be required.

Statistical analysis

Statistical analysis was performed using Microsoft Excel 2016. Quantitative data comparison between groups was analyzed using two-sample student t-test. The level of significance was set at $p < 0.05$.

CONSORT

TRANSPARENT REPORTING of TRIALS

CONSORT 2010 Flow Diagram

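### Starting haemoglobin sets each patient's margin above the 9.5 transfusion trigger, yet the only stated comparison is a valid but unadjusted t-test; a baseline-adjusted estimate beside it would probably be more precise

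*Combined protocol and SAP*

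**What the plan says.** The Pre-operative evaluation section sets a floor: "Pre-operative blood transfusion was done as required to have Hb level of at least 9.5mg/dl". The Post-operative evaluation section sets the transfusion trigger at the same value, giving blood if the patient's "Hb level fell below 9.5 mg/dl". It also defines the primary outcome: "The requirement of number of units of blood transfusion post-operatively was recorded as a primary outcome measure".

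Haemoglobin otherwise appears in three places in that section:
- as a secondary outcome: "The secondary outcome measures included change in Haemoglobin level";
- in follow-up: "Patients of both groups were monitored by checking Haemoglobin (Hb) level as required";
- as a descriptive summary (mean, SD and range).

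Under Surgical intervention, "The random allocation of the patients to either group was done by one of the authors using a random number table". No stratification, blinding or placebo is described. The Statistical analysis section consists of the software (Excel 2016), the significance level and one method: "Quantitative data comparison between groups was analyzed using two-sample student t-test". It mentions no covariate, regression or ANCOVA.

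**The concern.** A patient's margin before transfusion is starting Hb minus 9.5. Someone who starts at 9.6 is transfused after almost any fall, whereas someone who starts at 13 must fall by more than 3.5. The trial's own rules thus tie starting Hb to the primary outcome, although the documents give no data on how strong the tie is.

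An unadjusted t-test leaves all variation in starting Hb in the error term. With 50 patients per arm, the treatment estimate is then noisier than it need be. The pre-operative rule and the change-in-Hb outcome both already call for a pre-operative reading, so the information to remove part of that noise should largely exist.

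**Working it through.** **The plan's own figure.** Inputs from Sample size calculation: rates 15% and 40%, two-sided alpha 0.05, power 80%. With pooled variance and no continuity correction:

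n = [1.960 × √(2 × 0.275 × 0.725) + 0.842 × √(0.15 × 0.85 + 0.40 × 0.60)]² / 0.25² = (1.238 + 0.510)² / 0.0625 ≈ 48.9, so 49 per group.

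Power is 80.1% at 49 per arm and 80.9% at 50. Which rate belongs to which arm makes no difference at 1:1. This calculation concerns the proportion transfused and says nothing about power for the number of units.

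**What adjustment can do in general.** If starting Hb has correlation ρ with the outcome, adjustment multiplies the residual variance by 1 − ρ². Starting from 80%, power becomes Φ(2.80/√(1 − ρ²) − 1.96):

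| ρ (assumed) | Variance factor | Power |
|---|---|---|
| 0.2 | 0.96 | 81.6% |
| 0.3 | 0.91 | 83.6% |
| 0.4 | 0.84 | 86.4% |
| 0.5 | 0.75 | 89.9% |

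**Simulation for any transfusion, 50 per arm.** The documents give no Hb distribution, so these inputs are assumptions: Hb before top-up with mean 11 to 12 and SD 0.8 to 1.5; SD of the fall 0.7 to 1.5; 9.5 read as g/dl; patients below 9.5 topped up to 9.5 or to 9.5–10.5; Hb recorded with error of SD 0.5. Mean falls were set so that 40% and 15% are transfused. The comparison is the pooled t-test against a linear model with HC3 errors, adjusting for Hb before top-up.

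| Scenario | t-test | Adjusted |
|---|---|---|
| Central (mean 11.5, SD 1.2, fall SD 1.0) | about 82% | about 90% |
| Central, 10% departures from the trigger either way | 81.9% | 84.8% |
| Weak (mean 11, SD 0.8, fall SD 1.5) | 81.1% | 83.3% |
| Weak, 10% departures | 81.5% | 81.1% |
| Strong (mean 12, SD 1.5, fall SD 0.7) | 82.2% | 95.3% |

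The rows with departures, once calibrated to 40% and 15%, imply a mean rise in Hb in the 15% arm, and the weak case at full adherence implies a slight one. They are therefore pessimistic extremes. With a covariate unrelated to outcome, adjustment lowers power from 81.5% to 80.2%. Type I error was 4.2–5.7% for the t-test and 3.9–5.3% adjusted, so neither analysis is invalid.

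**Units.** The documents state no rule converting an Hb deficit into units. If one unit is assumed for each whole or part Hb unit below 9.5, starting Hb correlates with units at about −0.34 to −0.74. Power is then 83–91% for the t-test and 88–99% adjusted. These figures are only as good as the assumed rule.

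**Chance imbalance is the same loss.** One SD of chance difference in mean starting Hb (0.16–0.32 g/dl in these scenarios) moves the risk difference by about 2 to 5.5 points. The unadjusted standard error is √(0.3675/50) = 0.0857, or 8.6 points. The squared ratios, (2/8.57)² ≈ 0.05 and (5.5/8.57)² ≈ 0.41, are close to the ends of the simulated within-arm R² (0.07 to 0.42). The shift is thus already inside the standard error.

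**Which Hb.** If allocation could influence pre-operative transfusion, Hb at incision is not a clean baseline. In an illustration with assumed top-up to 10.5 in controls and 9.5 in the TXA arm, adjusting for pre-incision Hb moved the risk difference by 2.1–3.7 points. Adjusting for pre-randomisation Hb moved it by under 0.1.

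**The case against.** The strongest reply is that nothing here is an error. An unadjusted comparison in a 1:1 randomised trial is an acceptable choice, and nothing in the documents is contradicted or miscalculated. That stands: the point is an improvement in efficiency.

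Second, the gain rests on assumed distributions and on transfusion following the trigger. Since "Patients of both groups were monitored by checking Haemoglobin (Hb) level as required" and no blinding is described, adherence may have been imperfect. This also stands. With 10% departures the central gain falls to about 3 points and the weak case shows none, so the range must start at about zero.

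Third, the power figures are for any transfusion, while the stated primary outcome is units. This stands too; any transfusion is a supporting outcome only.

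Fourth, recruitment ran from April 2017 to August 2018, and a document dated July 2021 describes the analysis in the past tense. Outcomes had most likely been seen, so power for the primary test can no longer be gained. That limits the benefit to a more precise supporting estimate but does not remove it.

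It might also be said that change in Hb already deals with baseline. It does not: it is a separate secondary outcome and leaves the comparison of units unadjusted.

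**Conclusion.** The point holds as a modest improvement of low to moderate priority. The shared 9.5 value makes starting Hb a probable predictor of units transfused, and the plan makes no use of it in the primary comparison. Under the stated assumptions and for any transfusion, adjustment is worth from about 0 to about 13 points of power, with about 3 to 9 in a central case. The downside is about 1 point if Hb predicts nothing.

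A reader might infer three stronger things that the documents do not support:
- **The t-test is biased or invalid.** Randomisation protects it, and its simulated type I error is close to 5%.
- **The sample size is wrong, or the units analysis is shown to be adequately powered.** The 49 reproduces, but for two proportions; it bears on neither claim about units.
- **Chance imbalance in starting Hb is a second harm.** It is the precision loss seen from another side.

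**What to change.** Keep the t-test on units as the primary analysis. Beside it:

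1. Report a regression of units on arm and the last Hb recorded before randomisation, with a robust 95% CI.
2. Report any transfusion the same way, as a supporting outcome and not as primary.
3. Use Hb at incision instead only if it is confirmed that allocation could not have influenced pre-operative transfusion. The documents do not give the order of allocation, Hb testing and top-up.
4. Analyse change in Hb by ANCOVA on the same baseline. Post-operative transfusion alters later Hb, so state which post-operative reading is used, for example the last before any transfusion.
5. If outcomes had been seen when these analyses were specified, label them post hoc sensitivity analyses.

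The cost is a little extra analysis work and free software beyond Excel for the robust intervals. The existence and timing of a pre-randomisation Hb must be confirmed for all 100 patients, and missing values reported. No new patients or procedures are needed, and no clinical rule changes.

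### Change in haemoglobin appears to be compared by a t-test that ignores pre-operative Hb; the test is valid, but precision may be lost, by an amount that depends on which post-operative reading is used

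*Combined protocol and SAP*

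**What the plan says.** Under Post-operative evaluation the plan lists the secondary outcomes: "The secondary outcome measures included change in Haemoglobin level, total length of hospital stay", and evidence of deep vein thrombosis. Under Statistical analysis, the whole provision for comparing continuous outcomes is "Quantitative data comparison between groups was analyzed using two-sample student t-test". No covariate, model or adjusted estimate is mentioned.

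Two rules tie Hb to the value 9.5. Before surgery: "Pre-operative blood transfusion was done as required to have Hb level of at least 9.5mg/dl". After surgery: "The post-operative blood transfusion was done if the patients' Hb level fell below 9.5 mg/dl".

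On measurement, the Pre-operative evaluation section says "The enrolled patients were assessed preoperatively and all relevant investigations done". For follow-up, "Patients of both groups were monitored by checking Haemoglobin (Hb) level as required", with no fixed time. The readings are to be summarised by mean, SD and range. The plan does not define the formula for the change, the readings that enter it, or how a reading taken after a transfusion is treated.

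**The concern.** Pre-operative Hb is not listed as a data item, but it has to exist: the floor cannot be applied without it, and a change needs a starting value. The plan therefore holds the natural covariate for this outcome and does not use it.

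Comparing raw changes is equivalent to fixing the slope of post-operative on pre-operative Hb at 1. The plan's own rules can push the real slope lower. Nobody enters surgery below 9.5, and anyone who drops below 9.5 afterwards is transfused. If the later reading counts, a patient who starts close to 9.5 can show little net fall, while one who starts high can show all of it. The change is then negatively correlated with the starting value, and an unadjusted test treats that predictable spread as noise.

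Hb change is the only laboratory measure of blood loss among the named outcomes, so its precision matters. Allocation was by random number table with no stratification stated, so a chance difference in starting Hb between arms is possible. With a slope below 1, the arm that starts higher tends on average to show the larger fall.

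**Working it through.** **The plan's own figure.** The only power calculation concerns transfusion requirement: 15% v 40%, "with a two-sided significance of 0.05 and a power of 80" per cent. With the pooled-variance formula, n = [1.960·√(2·0.275·0.725) + 0.842·√(0.40·0.60 + 0.15·0.85)]² / 0.25² = (1.238 + 0.510)² / 0.0625 ≈ 48.9, so 49 per group, as stated. It says nothing about Hb change, and this point does not affect it.

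**Inputs for Hb change.** From the documents: 50 per arm, two-sided 0.05, floor and trigger both at 9.5. Not in the documents, hence assumed: SDs, the pre/post correlation (rho), the mean fall, the treatment effect, and the rise in Hb per unit transfused.

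**Closed form.** Let k be the post-operative SD divided by the pre-operative SD. The variance of the ANCOVA treatment effect relative to that of the change-score t-test is

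ratio = k²(1 − rho²) / (k² + 1 − 2·rho·k).

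The denominator exceeds the numerator by (1 − rho·k)², and rho·k is the slope of post-operative on pre-operative Hb. Adjustment therefore gains nothing when the slope is 1, and more as it moves away from 1. For k = 1 the ratio is (1 + rho)/2. If the t-test had 80% power, ANCOVA would have power Φ(2.802/√ratio − 1.960):

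| rho | variance ratio | variance cut | ANCOVA power | n per arm for the t-test to match ANCOVA at 50 (50/ratio) |
|---|---|---|---|---|
| 0.3 | 0.65 | 35% | 93.5% | 77 |
| 0.5 | 0.75 | 25% | 89.9% | 67 |
| 0.7 | 0.85 | 15% | 86.0% | 59 |
| 0.9 | 0.95 | 5% | 82.0% | 53 |

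The equal-SD assumption matters. At rho 0.5 the ratio is 0.571 for k = 0.8 and 0.871 for k = 1.2.

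**Simulation of the floor and trigger.** 50 per arm; baseline raised to at least 9.5; fall with mean 2 and SD 1; true effect 0.5; each unit raises Hb by 1; patients below 9.5 after surgery topped up, and the topped-up reading used; 2,500 trials per row.

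| Baseline mean, SD (before floor) | Slope | Variance ratio | t-test power | ANCOVA power | Gain (points) | Mean estimated effect (true 0.5), ANCOVA |
|---|---|---|---|---|---|---|
| 11, 1.2 | 0.39 | 0.472 | 15.4% | 25.9% | 10.5 | 0.16 |
| 11, 1.6 | 0.48 | 0.472 | 16.0% | 26.0% | 10.0 | 0.17 |
| 12, 1.2 | 0.59 | 0.722 | 36.0% | 46.4% | 10.4 | 0.29 |
| 12, 1.6 | 0.62 | 0.667 | 31.0% | 43.3% | 12.3 | 0.29 |
| 13, 1.2 | 0.80 | 0.945 | 55.5% | 59.0% | 3.5 | 0.39 |
| 13, 1.6 | 0.77 | 0.884 | 46.8% | 53.6% | 6.8 | 0.37 |

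With no true effect, both methods reject in 4% to 6% of trials. With the post-operative top-up removed (mean 12, SD 1.5) the slope is 1.00 and power is 69.2% v 68.4%: no gain.

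Under a smaller fall (mean 1.8, SD 0.9; baseline SD 1.0 to 1.5; effect 0.4 to 0.5) the gain is about 6 to 15 points at baseline means 11.5 to 12, where baseline and change correlate at about −0.42 to −0.68. It is about 0 to 5 points at mean 13, and nil when readings precede any top-up and the fall does not depend on baseline.

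**The case against.** The strongest reply is that nothing here is an error. Randomisation makes the two-sample t-test valid, the simulated type I error is right for both methods, and the plan claims no power for Hb change. That stands. A reader might infer that the comparison is biased, or that the arm starting higher will show the larger fall whatever the treatment does. The documents support neither: with a slope below 1 there is only an average tendency, a treatment effect can offset it, and chance imbalance is already covered by the test's error rate. Nor does the trial fall from 93.5% to 80% power; 80% is a reference point borrowed for illustration.

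Second, the raw post-minus-pre difference is an inference. The plan gives no formula and speaks of readings: "The Hb readings were expressed as mean", with SD and range. If post-operative readings were compared directly, (1 + rho)/2 would not apply. This stands as a limit on the size.

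Third, the simulated gain depends on using post-transfusion readings, which the plan neither requires nor excludes. It also depends on how often the trigger is met. The sample-size paragraph prints 15% for control and 40% for intervention, opposite to its stated aim of a reduction, so it is not a secure calibration and needs reconciling. It therefore cannot be stated as fact that power is lost.

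Fourth, masking is the larger problem: post-operative transfusion hides falls and shrinks a true 0.5 to between 0.16 and 0.39, and ANCOVA does not undo that. This stands too, and it is why the fix must name the reading. It is no argument against adjusting, which costs almost nothing under either choice.

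**Conclusion.** The point holds as a possible and avoidable loss of precision on one secondary outcome. It does not concern validity, the primary outcome or the sample size.

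The size cannot be fixed from the documents. With equal SDs, adjustment cuts the variance by 35% at rho 0.3 and by 5% at rho 0.9. With the floor and trigger simulated and post-transfusion readings used, the power gain is about 6 to 15 points when baseline Hb averages 11.5 to 12. At an average of 13 it is about 0 to 5 points under the smaller fall, and 3.5 to 6.8 under the larger. It is nil with pre-transfusion readings and a fall unrelated to baseline.

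These results rest on two inferences (that pre-operative Hb is recorded, and that change means post minus pre) and on the assumed Hb values. Because adjustment uses data already in hand and risks so little, it is worth making even though the gain may be small.

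**What to change.** In Statistical analysis, specify for this outcome a linear regression (ANCOVA) of post-operative Hb on treatment group and pre-operative Hb, and report the adjusted mean difference with its 95% confidence interval. Keep the raw mean change by group as a descriptive summary.

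In Post-operative evaluation, name the post-operative reading that enters the analysis, and say whether it precedes any post-operative transfusion. Without this the regression has no defined response, and it cannot recover falls masked by transfusion.

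The plan is dated July 2021 and recruitment ended in August 2018. If results are already known, label the ANCOVA as an added analysis and report it beside the t-test.

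The cost is a sentence or two in each of these sections, one regression that Excel can run, and one degree of freedom (100 − 3 = 97 instead of 100 − 2 = 98). No new data are needed, provided the chosen reading can be identified in the records.
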